	of the year, impute the first administration date of the next record - 1 day for the final administration date.
	Of note, if the final administration date is provided in the record where the final administration date of Humira has been identified according to the above rule and the "continued" checkbox is checked, follow the below:
	 If the described final administration date > the final administration date imputed according to the above rule, select the imputed final administration date as the final administration date of Humira for the patient. If the described final administration date <= the final administration date imputed according to the above rule, select the described final administration date as the final administration date of Humira for the patient.
	If the first administration date of Humira + 364 days < the final administration date of Humira imputed according to the above rule, select the first administration date of Humira + 364 days as the final administration date of Humira.
Days to the final administration date of Humira	The final administration date of Humira - the first administration date of Humira + 1
Administration status (dosage and administration)	Sort the data by the first administration date provided in "the administration status of Humira" in the survey form and aggregate the administration status (dosage and administration) according to the following rules: • If all the following [1] to [4] are satisfied, aggregate the data as "160mg→80mg→40mg once every two weeks and no changes thereafter". • If none of the following [1] to [4] is satisfied Aggregate as "others". [1] 1st administration: as a patient with a dose of 160mg

Data name	Derivation and calculation methods
	[2] 2nd administration: as a patient with a dose of 80mg
	[3] 3rd administration and thereafter: the dosing
	frequency "once every 2 weeks" is checked in the
	survey form, and a patient with a dose of 40mg
	* If the patient receives the third administration and
	thereafter, all the administration status should be the
	condition as shown in [3].
	[4] Patients who did not have a washout period for 30
	days or longer.
	If the administration status (dose and administration) is categorized
	in "others", follow the rules below to find the reason for the change
	in dose/dosing frequency.
	• 1st dose: "a reason for other than 160mg (a dose) or in the
	case of self-administration" in the survey form.

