Reason for change in	• 2nd dose: "a reason for other than 80mg (a dose) or in the case
dose/dosing frequency	of self-administration" in the survey form.
	• 3rd and the subsequent dose(s): "a reason for other than 40mg
	(a dose), or in the case of other than once every 2 weeks
	(dosing frequency)" or "reason for change in dose/dosing
	frequency" in the survey form.
	Dosing frequency
	[1] Sort data in the order of "the first administration date" of "the
	administration status of Humira", dosing frequency and
	description.
	[2] Calculate the dosing interval per data on administration status
	The interval between first and second administrations should
Administration status	be 14 days.
	• For the third and subsequent dose(s), the interval should be 14
(total number of dosing,	days if the dosing frequency "once every 2 weeks" is checked
total dose)	while the dosing frequency should be obtained from "[Humira
	UC] Conversion data provided for analysis" if the dosing
	frequency is "others".
	[3] Calculate the dosing frequency per data on administration
	status.
	Dosing frequency = (the final administration date (after
	imputed) – the first administration date(after imputed))/dosing

Data name	Derivation and calculation methods
	frequency (number of days)
	[4] When the results of [3] are ">0" (bigger than 0) and "<1"
	(smaller than 1), the dosing frequency shall be counted as 1.
	If the figure is ">=1" (1 or bigger), round the decimal down to the
	integer for the dosing frequency.
	[5] The total number of dosing shall be the total of [4] per patient.
	• Dose
	[1] If "Others" of a Humira dose is checked, the dose should be
	obtained from "[Humira UC] Conversion data provided for
	analysis".
	[2] Calculate the dose per data of the administration status.
	Dose = the number of dosing * a dose
	[3] The total dose should be the total of [2] per patient.
	• The mean daily dose
	The mean daily dose = the total dose/the total number of dosing
	If a patient's final administration date of Humira comes before the
	first administration date of Humira + 336, we handle the patient as a
Discontinued patients	discontinued case.
	Follow the above definition, no matter whether the discontinuation is
	selected in the survey form.
	"Present" is defined for the situation where a patient qualifies for the
	defined discontinued case and at least one has been checked in
Presence/absence of	"reason for discontinuation" of "discontinuation of the survey" of the

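### The SAP dose count is one injection short for a 14-day-interval record spanning 14 days or more, when its final date is the last injection or the day before an on-schedule next record

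*SAP*

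**What the plan says.** The rule is in SAP 10.1, Administration status (total number of dosing, total dose). The term dosing frequency is used there both for the interval in days and for the resulting count. Step [3] sets the count for each record as "Dosing frequency = (the final administration date (after" imputation) minus "the first administration date(after imputed))/dosing" interval. The interval is 14 days when the two-weekly box is ticked. Step [4] then has two branches. For a ratio above 0 and "smaller than 1), the dosing frequency shall be counted as 1". For a ratio of "1 or bigger), round the decimal down to the" whole number. Step [5] sums the record counts per patient. Total dose is record count times dose, summed, and the mean daily dose is total dose divided by total count.

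Two visible rules in the same section shape the final date. Where a date imputed as year end would overrun the next record, the SAP says to "impute the first administration date of the next record - 1 day for the final administration date". A patient-level cut-off says to "select the first administration date of Humira + 364 days as the final administration date of Humira", which is Day 365.

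The count and total dose are tabulated in Table 1.6 by the strata of SAP 11: 1–4, 5–12, 13–24 and 25 or more doses; 40–500, 501–1000 and 1001 mg or more. Table 2.3 uses the mean in item (14) and the count in item (17).

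**The concern.** A difference between two dates divided by the interval gives the number of gaps, and n injections have n − 1 gaps. Injections on Day 29 and Day 43 are 14 days apart: the ratio is 1 and the count is 1, although two injections were given. The item Days to the final administration date, also in SAP 10.1, includes both ends by adding 1; the dose count does not.

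A record whose first and final dates coincide gives a ratio of 0, and neither branch of step [4] assigns it a value.

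At stake are descriptive exposure figures: dose counts, total dose, their strata and the mean dose per administration. Splitting the same treatment into more records can also lower the reported exposure, because the shortfall is taken once per affected record.

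**Working it through.** The documents state no dose count that could be reproduced, so the rule is applied as written.

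**Inputs.** Interval 14 days (SAP 10.1). Doses follow the SAP's own reference category of 160, 80, then 40 mg every two weeks, used only to illustrate the counting. Assumptions: first and second records count as 1 each, later injections start on Day 29, and all injections are on schedule.

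**General result for a record of n injections, n ≥ 2.**
- Final date is the last injection: difference 14(n − 1); rule gives n − 1.
- Final date is the day before an on-schedule next record: difference 14n − 1; floor((14n − 1)/14) = n − 1.
- In general, an end date 0–13 days after the last injection gives a count one short (span 14 days or more), 14–27 days gives the right count, and 28 days or more gives too high a count.

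**One later record from Day 29, final date = last injection.** Possible days are 43, 57, …, 365, that is (365 − 43)/14 + 1 = 24. Each is one dose and 40 mg short. The stratum is wrong on five:

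| Final date | Difference | Later doses, rule / given | Total count, rule / given | Total dose (mg), rule / given | Stratum error |
|---|---|---|---|---|---|
| Day 57 | 28 | 2 / 3 | 4 / 5 | 320 / 360 | count 1–4, not 5–12 |
| Day 113 | 84 | 6 / 7 | 8 / 9 | 480 / 520 | dose 40–500, not 501–1000 |
| Day 169 | 140 | 10 / 11 | 12 / 13 | 640 / 680 | count 5–12, not 13–24 |
| Day 295 | 266 | 19 / 20 | 21 / 22 | 1000 / 1040 | dose 501–1000, not 1001 or more |
| Day 337 | 308 | 22 / 23 | 24 / 25 | 1120 / 1160 | count 13–24, not 25 or more |

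Mean dose at Day 57: 320/4 = 80.0 instead of 360/5 = 72.0 mg. At Day 337: 1120/24 = 46.67 instead of 1160/25 = 46.40 mg. A patient ending on Day 337 is not discontinued under SAP 10.1, because the final date is not before the "first administration date of Humira + 336, we handle the patient as a" discontinued case, yet misses the top count stratum. If the later record holds only the Day 29 injection, the difference is 0 and step [4] gives no value.

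**Full-year patient cut off at Day 365, no injection that day (26 given), with the cut-off carried into the last record.**
- One later record: 336/14 = 24; 1 + 1 + 24 = 26, right.
- Two (Days 29–168, 169–365): floor(139/14) + 196/14 = 9 + 14; total 25, same stratum.
- Three (Days 29–112, 113–224, 225–365): floor(83/14) + floor(111/14) + floor(140/14) = 5 + 7 + 10; total 24, stratum 13–24 instead of 25 or more.

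**Adding 1 after rounding down.** Both cases in the general result then return n, and a difference of 0 gives 1. Applying it only to records ended the day before the next one repairs the split examples: 2 + 10 + 14 = 26 and 2 + 6 + 8 + 10 = 26. With a shared boundary date (Days 29–113 and 113–197, 13 later doses) the present rule gives 6 + 6 = 12 and adding 1 alone gives 7 + 7 = 14. Ending the first record on Day 112 gives 6 + 7 = 13.

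**The case against.** The strongest reply is that the count depends on what a record's final date means, and part of that definition is not in the supplied text. What is visible partly suggests an end-of-coverage date. From the third dose the form records an administration period (Protocol 8(3), item 5). The SAP imputes year-end dates, refers to a continued checkbox and caps the patient at Day 365. The day-before-next-record rule is visible only as a fallback for an overrunning year-end date. If the final date is a full interval after the last injection, the present rule is right.

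This stands as a limit on how often the error occurs, not as a rebuttal. The field is named as an administration date, and the SAP runs its 14-day assessment window (12.3 to 12.6) and 28-day safety window (section 2) from it in discontinued patients. That fits a last injection, and these are the patients for whom a reported last injection is most likely to be used.

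Late or skipped doses also stand. If the next record starts 1–14 days late the rule is right; from 15 days late it overcounts. The SAP foresees gaps: its reference category requires "4] Patients who did not have a washout period for 30" days or longer.

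A reader might go further and infer that exposure in the survey is understated overall, or that the rule fails on nearly every possible end day. The documents support neither. The direction varies with the end date, and calendar days are not patients: only the 24 injection days qualify under the schedule assumed. Nor do they establish that a patient with a single injection scores zero doses, since how the first record's dates are completed is not visible.

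**Conclusion.** The point holds conditionally. For a 14-day interval, injections on schedule and a span of 14 days or more, a record ending on its last injection, or the day before an on-schedule next record, is counted one injection short. In the one-later-record example that is one dose and 40 mg, with a stratum error on 5 of 24 possible last-injection days. Over several records the shortfall accumulates. The gap at a difference of 0 exists as written.

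The rule is already right for a patient with one later record cut off at Day 365 without an injection that day, and for a coverage end date one full interval after the last injection. How often each case occurs, and the net direction in the real data, cannot be determined from the documents.

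The consequence is small and descriptive, confined to Table 1.6 and Table 2.3 items (14) and (17). No test, days-of-administration figure or Kaplan-Meier continuation rate changes, and no dosing rule is involved. It should be corrected because the stated rule gives a wrong number in the cases described and the repair is simple.

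**What to change.** In SAP 10.1, steps [3] and [4]:

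- Where a record's final date is a reported last injection, or is set to the day before the next record, use floor(difference/interval) + 1. This also gives 1 when the difference is 0.
- Where a record is ended by the Day 365 cut-off or by a coverage end date, keep floor(difference/interval) with a minimum of 1. Adding 1 everywhere would turn the correct 26 of the full-year patient with one later record into 27.
- Where two records share a boundary date, end the preceding one a day before.
- State that the count is derived on the assumption of injections on schedule. With late or skipped doses neither formula is reliable: when a next record starts 1–14 days late, the added 1 itself overcounts by one.

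Then re-run Table 1.6 and Table 2.3 items (14) and (17). The cost is a few lines of SAP text, a small code change and two re-run outputs. The change needs each end date classed as reported injection, day-before-next, coverage end or cut-off. The protocol's list of form items does not show individual injection dates from the third dose, so one stated convention for reported dates will be needed.

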reason for	survey form. On the other hand, if a patient qualifies for the defined
discontinuation	discontinued case and no description has been made in the "reason
	for discontinuation" column in the survey form, the case is defined as
	an "unknown/not provided" case.
	It should derive from "reason for discontinuation" of
Reason for	"discontinuation of the survey" of the survey form. Recode the
discontinuation	reason for discontinuation based on other descriptions of "reason for
discontinuation	discontinuation" and "[Humira UC] Conversion data provided for
	analysis". Select "unknown/not provided" for undescribed data".
Reason for	Obtain the detailed items of reason for discontinuation "others" in
discontinuation, other	"[Humira UC] Conversion data provided for analysis".
reasons	
Patients who continue	The patients who are not the discontinued cases are regarded as the

Data name	Derivation and calculation methods
the survey	patients who continue the survey
Presence/absence of	When complication data are contained in the survey form, it should
	be classified as "with complications". When there is no description of
	"presence/absence of complications" in the survey form or the
complications	assessment is impossible, it should be classified as "unknown/not
	provided", and other cases are "no complications".
	When medical-history data are contained in the survey form, it
Presence/absence of	should be classified as "with medical history". When there is no
	description of "presence/absence of medical history" in the survey
medical history	form or the assessment is impossible, it should be classified as
	"unknown/not provided", and other cases are "no medical history".
Complication/Hepatic	When hepatic function disorder data are contained in "171210
function disorder	Complication", it should be classified as "with hepatic function
Tunction disorder	disorder". other cases are "no hepatic function disorder".
Complication/Renal	When renal impairment data are contained in "171210
impairment	Complication", it should be classified as "with renal impairment".
ппрантнени	other cases are "no renal impairment".
Presence/absence of	When circulatory disorder data are contained in "171210
Complication/Circulator	Complication", it should be classified as "with circulatory disorder".
y disorder	other cases are "no circulatory disorder".
Presence/absence of	When blood disorder data are contained in "171210 Complication", it

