Complication/Blood	should be classified as "with blood disorder. Other cases are "no
disorder	disorder".
Presence/absence of	When respiratory disorder data are contained in "171210
Complication/Respiratory	Complication", it should be classified as "with respiratory disorder.
disorder	Other cases are "no respiratory disorder".
	If a survey form contains the data other than hepatic function
	disorder, renal impairment, circulatory disorder, blood disorder and
	respiratory disorder, it should be classified as "with other
	complications". Others are "no other complications".
Presence/absence of	
Complication/others	If a survey form contains the data in "171210 Complication" for
	presence/absence of diabetes mellitus, gastrointestinal disorder,
	osteoporosis and malignant tumour as well among the detailed
	classifications of other complications, it should be classified as "with
	complications". Others are "no complications".

Data name	Derivation and calculation methods
	If a survey form contains the data on complications other than
	diabetes mellitus, gastrointestinal disorder, osteoporosis and
	malignant tumour among the detailed classifications of other
	complications, it should be classified as "with other complication of
	other detailed classifications". Others are "no other complication of
	other detailed classifications".
	As for collagen disorder, if "other: collagen disorder" in
	"complications" of "patient information" is checked, it should be
	classified as "with collage disorder. Other cases are "no collagen
	disorder".
Medical history:	When tuberculosis data are contained in "180111 Medical history", it
presence/absence of	should be classified as "with tuberculosis. Other cases are "no
tuberculosis	tuberculosis".
Medical history:	When non-tuberculous mycobacteriosis data are contained in
presence/absence of	"180111 Medical history", it should be classified as "with
non-tuberculous	non-tuberculous mycobacteriosis. Other cases are "no
mycobacteriosis	non-tuberculous mycobacteriosis".
Medical history:	When interstitial pneumonia data are contained in "180111 Medical
presence/absence of	history", it should be classified as "with interstitial pneumonia. Other
interstitial pneumonia	cases are "no interstitial pneumonia".
Medical history:	When bronchitis bacterial data are contained in "180111 Medical
presence/absence of	history", it should be classified as "with bronchitis bacterial. Other
bronchitis bacterial	cases are "no bronchitis bacterial".

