discontinuation, other	the condition improved, the condition worsened
reasons	Poor adherence, for study
Sex	Man, women, unknown/not provided
Pregnancy/nursing	Not pregnant/nursing, pregnant, nursing, unknown/not provided
Race	Japanese, other Asians, others, unknown/not provided
Age (in years)	$<15, \ge 15$ and $<65, \ge 65$, unknown/not provided
	<30, ≥30 and <40, ≥40 and <50, ≥50 and <60, ≥60, unknown/not
Body weight (kg)	provided
BMI(kg/m ²)	$<18.5, \ge 18.5 \text{ and } <25, \ge 25 \text{ and } <30, \ge 30, \text{ unknown}$
Duration of illness (in	
years)	$<2, \ge 2$ and $<10, \ge 10$, unknown/not provided
Indication (registration	Colitis ulcerative, others, not provided
form)	

Data	How to stratify
Allergy history	Without the history, with the history, unknown/not provided
Smoking history	Without the history, with the history, unknown/not provided
Detailed classification of smoking history	Smoking, only in the past (not smoking now), unknown
Tuberculosis test	Not conducted, conducted
Hepatitis B test	Not conducted, conducted
Complications	Without the history, with the history, unknown/not provided
Detailed classification of complications	Liver disorder, renal disorder, blood disorder, respiratory disorder, others
Other classification of complications	Diabetes mellitus, osteoporosis, malignant tumour, others
Medical history	Without the history, with the history, unknown/not provided
Detailed classification of medical history	Tuberculosis, non-tuberculous mycobacteriosis, interstitial pneumonia, bronchitis bacterial, aplastic anaemia, pancytopenia, malignant tumour, others
Prior medications for colitis ulcerative	Without the history, with the history, unknown/not provided
Details classification of	Infliximab, other biological products, aminosalicylic acid products,
prior medications for	corticosteroid, azathioprine & 6-mercaptopurine, tacrolimus &
colitis ulcerative	ciclosporin, antibiotics, prior medication: others
Prior treatment for colitis ulcerative	Without the history, with the history, unknown/not provided
Details classification of prior treatment for colitis ulcerative	Leukocytapheresis, surgery, enteral nutrition therapy, intravenous nutrition therapy, others
Treatment history with biological products	Without the history, with the history, unknown/not provided

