Age (year), the elderly, pediatrics, sex, body weight (kg), BMI (kg/m²), duration of illness (year), complications, complication: hepatic function disorder, complication; renal impairment, complication: blood disorder, complication: respiratory disorder, complication: diabetes mellitus, complication: osteoporosis, complication: malignant tumour, medical history, medical history: tuberculosis, medical history: non-tuberculous mycobacteriosis, medical history: interstitial pneumonia, medical history: bronchitis bacterial, medical history: aplastic anaemia, medical history: pancytopenia, medical history: malignant tumour, allergy history, smoking history, detailed history of smoking history, the administration status of Humira: self-administration, prior medication, prior medication: biological product, prior medication Infliximab, prior medication: other biological product, prior medication: aminosalicylic acid drug, prior medication: corticosteroids, prior medication: azathioprine, prior medication 6-mercaptopurine, prior medication: azathioprine & 6-mercaptopurine, prior medication: tacrolimus & ciclosporin, prior treatment, prior treatment: leukocytapheresis, prior treatment: surgery, prior treatment: enteral nutrition therapy, prior treatment: intravenous nutrition therapy, concomitant medication, concomitant medication: aminosalicylic acid drug, concomitant medication: corticosteroids, concomitant medication: azathioprine, concomitant medication: 6-mercaptopurine, concomitant medication: azathioprine & 6-mercaptopurine, concomitant medication: tacrolimus & ciclosporin, concomitant treatment, concomitant treatment: leukocytapheresis, concomitant treatment: surgery, concomitant treatment: intravenous nutrition therapy, concomitant treatment: enteral nutrition therapy, site of disease by type, partial Mayo score, CRP

"2.9.xx Incidence of adverse reactions per background factor and seriousness"

Patients for analysis: patients in the safety analysis group

Analysis objective: to show the onset status of non-serious/serious adverse reactions per statistically-significant background factor based on the test results in 2.9.

Analysis item: aggregate the following items per background factor and seriousness for adverse reactions which occurred in the safety analysis period.

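### SAP 10.1 and Section 11 disagree on the residual complication classes, so *others* in Table 1.12 is undercounted and some patients fall into no row of the breakdown

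*SAP*

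**What the plan says.** SAP 10.1 sets up complications in layers.

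- **Overall item.** Any recorded complication makes the patient positive: "When complication data are contained in the survey form, it should" be classed as with complications.
- **Organ classes.** Hepatic, renal, circulatory, blood and respiratory disorder are each derived from the coded complication file. The circulatory flag is still among them: "When circulatory disorder data are contained in" that file, the patient is positive.
- **First-level residual.** The Complication/others rule takes data other than hepatic function "disorder, renal impairment, circulatory disorder, blood disorder and" respiratory disorder.
- **Second-level residual.** Within *others*, the same rule takes complications other than "diabetes mellitus, gastrointestinal disorder, osteoporosis and" malignant tumour.

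Section 11 gives the classes to be displayed. The detailed classification is "Liver disorder, renal disorder, blood disorder, respiratory disorder, others". The other classification is "Diabetes mellitus, osteoporosis, malignant tumour, others". Table 1.12 counts patients by the Section 11 segments, in the safety group, the effectiveness group and the patients with locked forms. Its note allows patients to be counted more than once in these classifications.

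Table 2.9 tests the overall complications item and a list of single classes, including "complication; renal impairment, complication: blood disorder, complication: respiratory disorder". Tables 3.4 and 3.4.1 use the same complication factors. Circulatory disorder, gastrointestinal disorder and *others* are not on the list.

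**The concern.** A residual class should hold whatever the displayed rows do not. Here the residual is defined against a longer list of classes (10.1) than the list displayed (Section 11). Any class on the first list but not on the second has nowhere to go: it is barred from *others* and has no row of its own.

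What is at stake is the accuracy and reproducibility of a reported count. A programmer who follows 10.1 and one who reads *others* in Section 11 as the remainder of the rows shown would obtain different numbers. The table would not reveal the difference: because its rows may overlap, they need not sum to the overall item, so a shortfall cannot be seen.

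**Working it through.** The plan states no figure on this point, so the check is one of classification. The inputs are the two residual rules in SAP 10.1 and the two class lists in SAP Section 11.

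1. Classes barred from first-level *others* (10.1): hepatic, renal, circulatory, blood, respiratory. First-level rows displayed (Section 11): liver, renal, blood, respiratory, *others*. Barred but not displayed: **circulatory**.
2. Classes barred from second-level *others* (10.1): diabetes mellitus, gastrointestinal, osteoporosis, malignant tumour. Second-level rows displayed (Section 11): diabetes mellitus, osteoporosis, malignant tumour, *others*. Barred but not displayed: **gastrointestinal**.

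Passing a patient with one complication through the rules as written, and again with the two terms removed from the exclusions, gives:

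| Only complication | Overall item | First level, as written | Second level, as written | First level, aligned | Second level, aligned |
|---|---|---|---|---|---|
| Hepatic, renal, blood or respiratory | with | own row | not applicable | own row | not applicable |
| Circulatory | with | **none** | **none** | others | others |
| Gastrointestinal | with | others | **none** | others | others |
| Diabetes, osteoporosis or malignant tumour | with | others | own row | others | own row |
| Collagen disorder | with | others | others | others | others |
| Any unlisted condition | with | others | others | others | others |

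Collagen disorder is a useful control. It has no row in Section 11 either, but 10.1 does not bar it from the residual, so it lands in *others* at both levels. The cause is therefore the two leftover exclusions, not the absence of a row.

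Patients with more than one complication show why *others* is undercounted beyond the single-complication cases. Someone with a hepatic and a circulatory disorder appears in the liver row, but the circulatory disorder is counted in no row. Measured against the rows shown, that patient also belongs in *others*.

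None of the tested factors in Tables 2.9, 3.4 and 3.4.1 is a residual class, so changing who falls into *others* alters no planned test.

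**The case against.** The strongest reply is that leaving these rows out was deliberate. The SAP revision history for version 1.1 records their removal from Section 11, and the current factor lists agree with it. Nothing in the protocol requires a circulatory row or a circulatory factor. That stands, and the choice of rows is the sponsor's. It does not answer the point, because once a row is dropped the residual has to absorb its patients, and the current 10.1 rule still prevents that.

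Three stronger readings are tempting, and the documents do not support them.

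- *Table 1.12 understates complications as a whole, or gastrointestinal patients fall into no class.* Both groups are counted in the overall complications item. The first-level exclusions do not name gastrointestinal disorder, so gastrointestinal-only patients do appear in first-level *others*.
- *Circulatory comorbidity is displayed nowhere.* It has no row in Table 1.12, but complications are listed patient by patient as MedDRA preferred terms in Table 1.4.1 (beside the adverse events), in Table 1.4.4 (ages 18 and under) and in item 11 of Table 2.3.
- *A circulatory factor must be added because congestive cardiac failure is a priority item.* Table 2.9 tests the occurrence of any adverse reaction, so the added factor would not examine cardiac failure. Which exploratory factors to test is a preference, and the overall complications item is already tested.

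**Conclusion.** The two sections conflict in the current text, and following the SAP literally gives a wrong count of *others*. Circulatory-only patients have no detailed row at either level; gastrointestinal-only patients lack only a second-level row. The consequence is limited to the descriptive breakdown in Table 1.12, and the point is minor.

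The size cannot be computed. The documents give no prevalence for either class, and which terms count as circulatory or gastrointestinal depends on a coding file that is not reproduced. A reader might apply an assumed prevalence to the target sample: 1500 × 3%, 5% or 10% = 45, 75 or 150 patients. Those products count patients with any circulatory complication. The patients in no row are only those with no complication in a displayed class, so under each assumption the product is a ceiling and not an estimate.

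The conclusion rests on reading the 10.1 rule as written, and on Table 1.12 using the Section 11 classes, as the SAP says it does.

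**What to change.** In the Complication/others rule of SAP 10.1, delete circulatory disorder from the first-level exclusion list and gastrointestinal disorder from the second-level exclusion list. As the last two columns of the table above show, every single-complication patient then has a row. The sentence in 10.1 that derives gastrointestinal disorder as a class, and the separate circulatory flag, exclude nothing and can stay.

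The cost is two deleted terms, a line in the revision history and a rerun of Table 1.12. Restoring both rows in Section 11 would also close the gap, but it would reverse a recorded choice and is not needed to correct the count.
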